9.1.3 General conventions

Descriptive statistics for parameters of interest will be provided by treatment group (pooled DT groups, DT 20 mg/m² alone, DT 30 mg/m² alone and BSC control group) and overall.

The baseline value will be defined as the last available value prior to first DT infusion for patients in tested dose groups or prior to first BSC administration for patients in BSC.

The type I (α) error will to be 5% (two-sided) for all analyses.

From a statistical point of view, this study will not be comparative between the two doses of DT. So comparison of confidence intervals between each DT group versus BSC will be exploratory in order to define the benefit-risk ratio for each dose (see 9.6).

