
Safety measures:
 
For patients randomised in the DT groups:
 
Premedication will be administered during three consecutive days starting one day before DT administration. It will consist of methylprednisolone 32 mg (or equivalent) + cetirizine 20 mg (or equivalent) per day.
 
SaO₂ will be monitored during 24 hours as follows:
 
 ○ During the 6-hour DT infusion 
 - Continuous monitoring of SaO₂: 
 ▪ If SaO₂ < 93% → reduction of DT infusion rate by half. No changes in dose; ▪ If SaO₂ ≤ 90% → immediate and definitive infusion stop; - Monitoring of respiratory symptoms: 
 ▪ In case of a respiratory symptom (dyspnoea, increase in respiratory rate by 5 beats/min and RR > 20/min) → reduction of DT infusion rate by half. No changes in dose; ▪ In case of persistence of symptoms within 1 hour → immediate and definitive infusion stop. ○ After the end of DT infusion. 
 - In case of marked decrease in SaO₂ or occurrence of respiratory symptoms, the patient should be transferred to intensive care unit for monitoring and treatment up to recovery. 
In case of SaO₂ decrease (≤ 90%) during or after DT infusion, SaO₂ will be closely monitored and collected every hour until resolution to SaO₂ ≥ 93%.
 
Patients with a respiratory adverse event during a previous DT infusion who remain eligible to continue DT treatment will have reinforced respiratory safety measures for each additional DT infusions and SaO₂ collected every hour during infusion and within the 6 hours after the end of infusion.
 
The recommended treatment of drug-induced pneumonitis is based on systemic corticosteroids with methylprednisolone 1 g/day for 3 days in patients with respiratory failure or lower doses of corticosteroids (i.e
		

NAME OF COMPANY: Onxeo (formerly known as BioAlliance Pharma)	NAME OF FINISHED PRODUCT: Doxorubicin Transdrug™ 10 mg	NAME OF ACTIVE INGREDIENT: Doxorubicin

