Actually the population expected in the ReLive study will be markedly different from the population observed in the DOTAHCC1 study. Patients are expected to be more severe and consequently the median survival time of the control group should be markedly lower. A Korean study conducted on a population closer to the one expected for ReLive study has reported a median survival time of 187 days (Woo H.Y., 2011^[50]). Under an exponential distribution, a median survival time of 187 days would correspond to a 1-year survival rate of 25.8% (2-year survival rate of 6.7%). A French cohort study conducted on 1287 naive patients with HCC reported that only 187 patients were eligible for Sorafenib treatment and 103 received Sorafenib in whom a 1-year survival of 16% was reported (Rosa L., 2011^[27]). Under an exponential distribution, a 1-year survival rate of 16% would correspond to a median survival time of 138 days and to a 2-year survival rate of 2.6%.

Following the publication of the positive RESORCE regorafenib phase 3 study in Child Pugh A patients tolerant and progressing under sorafenib, the SAP was revised in order to handle the potential risk of lack of power. Analysis of efficacy and safety of the pooled DT groups versus BSC group was chosen as primary analysis and a more realistic OS in the control group of 8 months instead of 6.6 months (200 days) and an HR of 0.69 instead of 0.60 were considered. Following the recent data of prospective non interventional studies showing that the Child Pugh status is a strong prognostic factor for OS in patients treated by sorafenib (median OS of 13 months in Child Pugh A patients versus 5 months in Child Pugh B), analysis of efficacy and safety in this homogeneous population of Child Pugh A patients from whom the clinical benefit is expected to be higher has been added. An OS in the control group of 9 months and an HR of 0.68 were considered in this population.

The hierarchical sequential closed test procedure will be used to control the overall type I error rate of 5% to evaluate first the primary endpoint OS in the ITT population, then if statistically significant the primary endpoint OS in the ITT Child Pugh A population and then if statistically significant the main secondary endpoints (PFS and OOR) in the ITT Child Pugh A population.

The following sequence will be followed:

- OS in the overall ITT population
- OS in the ITT Child Pugh A population
- PFS in the ITT Child Pugh A population

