- ORR in the ITT Child Pugh A population

Overall population:

Under the assumptions of a median survival of the control group of 8 months and a hazard ratio of 0.69, the required total sample size to achieve a 85% power to compare the experimental groups (pooled DT 20mg/m² and DT 30mg/m²) versus BSC and performed at a significance level of 2.5% one sided is 348 patients in the ITT population (116 patients in the BSC group

and 232 patients in the DT group). It is expected 10% of patients will be lost to follow-up; this leads to a calculated total sample size of 390 randomised patients.

Child Pugh A population (85% of the patient population):

Under the assumptions of a median survival of the control group of 9 months and a hazard ratio of 0.68, the required total sample size to achieve a 80% power to compare the experimental group (pooled DT 20mg/m² and DT 30mg/m² groups) versus BSC with a significance level of 2.5% one sided is 291 patients in the ITT Child Pugh A population (97 patients in the BSC group and 194 patients in DT groups). It is expected that 10% of patients will be lost to follow-up; this leads to a calculated total sample size of 324 ITT Child Pugh A randomised patients.

Thus the study will be completed once a total of 390 patients will have been randomized. The analysis will be performed when 285 events have occurred (corresponding to 230 events in the ITT Child Pugh A population).

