9.2 Population to be analyzed

The Safety Population is defined as all included subjects receiving at least one DT infusion or at least one anti-cancer therapy or supportive care as BSC. For safety analyses, patients will be affected to the group of treatment they actually received.

The following populations are planned for the efficacy analyses:

- The Intent To Treat (ITT) Population : all randomized patients. In this population, patients will be analysed in their randomisation group whatever the treatment they received.
- The Per Protocol (PP) population includes all the patients of the ITT population without any major protocol deviation. Patients terminating the study prematurely will be included in the PP population provided that there is no protocol deviation. Before locking the database, the precise reasons for excluding patients from the PP dataset will be fully defined and documented by the Blind Review Committee.

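### Section 9.1.3 sets baseline by first treatment, differently in each arm, although ITT analyses start at randomisation: a cheap correction for efficacy covariates and, if it sets Child-Pugh class, for the Child-Pugh A subset

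*Combined protocol and SAP*

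**What the plan says.** Section 9.1.3 gives the only visible analysis rule for baseline. For the DT arms: "The baseline value will be defined as the last available value prior to first DT infusion for patients in tested dose groups". For the control arm, the value is the last one "prior to first BSC administration for patients in BSC".

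Section 9.2 defines three populations. For efficacy: "The Intent To Treat (ITT) Population : all randomized patients", analysed as randomised whatever they received. The Safety population is narrower: "all included subjects receiving at least one DT infusion or at least one anti-cancer therapy or supportive care as BSC". Per Protocol is the third. Section 9.4.1 measures OS from the date of randomisation.

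Section 9.1.2 orders four tests: OS in overall ITT, OS in ITT Child-Pugh A, "PFS in the ITT Child Pugh A population", and ORR in the same subset. Section 9.2 does not define that subset, and no visible text says which Child-Pugh assessment decides membership. Randomisation is stratified by region only (section 4.3), so no visible stratum fixes the class. Section 7.1 records Child-Pugh at screening for all groups. Section 9.1.1 defers further detail to a separate SAP, which is not among the documents.

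**The concern.** Baseline covariates in an ITT model, and membership of a subset labelled ITT, should rest on information obtained before allocation, by one rule in every arm. Section 9.1.3 departs from this in three ways.

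- **The anchor differs by arm and can fall after allocation.** DT premedication is listed only for patients randomised to DT (Synopsis, Safety measures): "Premedication will be administered during three consecutive days starting one day before DT administration". Allocation is therefore known by D0, while the anchor is the D1 infusion. A value taken after allocation, and after study premedication has begun, still counts as baseline. BSC has no equivalent.
- **The BSC anchor has no visible limit.** Under section 6.4 the first BSC administration may be supportive care. Treatments and their dates are recorded (sections 6.5 and 6.8), but no visible text says how soon after randomisation BSC must start.
- **Never-treated patients have no anchor.** They remain in ITT, and the Safety definition foresees that they may exist.

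At stake are the adjusted sensitivity analyses of sections 9.4.1 and 9.4.2, which use covariates such as ECOG score, Child-Pugh score and prothrombin time. Tests 2 to 4 are also at stake, but only if the same rule is used to assign Child-Pugh class.

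**Working it through.** **1. The plan's own figure for the subset.** Inputs from section 9.1.2: 230 events, hazard ratio 0.68, pooled DT to BSC 2:1, two-sided 5%. Schoenfeld power = Φ(√(230 × 1/3 × 2/3) × |ln 0.68| − 1.96) = Φ(7.149 × 0.3857 − 1.96) = Φ(0.797) = 78.7%, against 80% stated. The sample size also reproduces: 291 / 0.9 = 323.3, rounded up to 324. The point concerns a definition, not these figures, and the fix leaves them unchanged.

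**2. The anchors side by side.**

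| | DT arms | BSC arm | Randomised, never treated |
|---|---|---|---|
| OS time origin (9.4.1) | randomisation | randomisation | randomisation |
| In ITT (9.2) | yes | yes | yes |
| Baseline anchor (9.1.3) | first infusion, D1 | first BSC of any kind | none |
| Gap from randomisation to anchor | probably about one day | no visible limit | not defined |

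The one-day figure comes from section 3, which describes randomisation after the D0 baseline visit. With infusion on D1, that leaves about one day.

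**3. Is a Child-Pugh class available between screening and first treatment?** Section 7.1 records the score at screening. The later check in section 6.6.2 concerns continuing treatment, and the Synopsis ties the same list to additional infusions. Section 7.6.3 requires liver function tests before each administration, but these are laboratory values, not a re-scored class. The contents of the cycle visits are redacted. On visible text, the last class before first treatment is the screening one. Laboratory and clinical covariates can be more recent.

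**4. Scope if 9.1.3 also sets class.** Three of the four sequenced tests use the subset, and the final analysis is described as "corresponding to 230 events in the ITT Child Pugh A population": 230 / 285 = 80.7% of planned events. This sizes the subset, not any misclassification.

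**5. Why class is prognostic.** For sorafenib-treated patients section 9.1.2 gives "median OS of 13 months in Child Pugh A patients versus 5 months in Child Pugh B". Under exponential survival the hazard ratio of B to A is 13 / 5 = 2.6. One-year survival is 0.5^(12/13) = 52.7% in A and 0.5^(12/5) = 18.9% in B. These medians describe class B as a whole (7 to 9 points, Appendix II). Eligibility here stops at B7, so the shift that matters is from A6 to B7, and 2.6 is not its measure.

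**6. Never-treated patients: illustration only.** Suppose they were dropped from the subset for want of a baseline. The documents give no rate, so 2%, 5% and 10% of class A patients and their events are assumed lost. Events fall from 230 to about 225, 218 and 207. By the formula in step 1, power for test 2 taken alone falls from 78.7% to 77.9%, 76.7% and 74.4%.

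**7. Age of a pre-randomisation value.** Screening runs to 28 + 2 = 30 days before D0 (sections 3 and 7.1).

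**The case against.** The strongest reply has four parts.

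- **The DT gap is about a day.** Section 3 supports this, and it stands as the probable reading. Any effect in those arms should be small, although premedication has started by then.
- **BSC follows the same visits.** The Synopsis puts control patients on the DT visit schedule, and section 6.5 requires visits on days 1 and 14. This gives a common structure for assessments but does not date the first BSC administration, which is the anchor.
- **The rule may never reach Child-Pugh class.** Section 9.1.3 does not mention class or population membership, and the separate SAP may define the subset and the handling of untreated patients. This stands. The absent definition of ITT Child-Pugh A, and the unstated assignment of patients without cirrhosis, are taken alone missing detail rather than an error.
- **The effect is unmeasured.** This also stands: the frequency of reclassification cannot be determined.

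A reader might infer that Child-Pugh is re-scored at D0 before the first infusion, so that the DT arms use a newer class than BSC. The visible text does not support that, because the D0 check is tied to continuing treatment and the listed criteria to additional infusions.

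A reader might also infer an inflated type I error for test 2. That would require an assumed rate of slippage from A to B7, an assumed survival after slippage, and detection in one arm only. The documents supply none of these, and even the direction would depend on which arm was assumed to detect it.

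**Conclusion.** The point holds in a limited form. As written, section 9.1.3 differs by arm, allows post-allocation values in an open-label trial, and leaves never-treated ITT patients without a baseline. It directly affects the laboratory and clinical covariates in the adjusted sensitivity models. Its effect on tests 2 to 4 is conditional on the rule also being used to set Child-Pugh class, and on visible text reclassification may be rare.

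No size of bias can be given. The 81% of events and the hazard ratio of 2.6 show why the class should be fixed before allocation is known; they do not measure an error. The power losses in step 6 rest on assumed rates. The primary OS test in overall ITT is unaffected, and no type I error inflation is claimed. The conclusion rests on visible text only, since the visit sections are redacted and the separate SAP is not available. Severity is low: a cheap improvement.

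**What to change.** **Section 9.1.3.** For efficacy covariates and subset membership, use in all arms the last value obtained before randomisation. Accept a value from the day of randomisation only if it was taken before allocation. Keep the last value before first treatment for safety change from baseline.

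**Section 9.2.** Add a definition such as: *ITT Child-Pugh A: all randomised patients in class A (5–6 points, Appendix II) on the last assessment obtained before randomisation, whether or not treated.* State one assignment for patients without cirrhosis, who are eligible under section 4.1 although section 6.6.2 applies the score only where cirrhosis is present. If the separate SAP already contains these rules, mirror them here.

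**Cost.** A few sentences and no new data: Child-Pugh is recorded at screening for all groups (section 7.1), and enrolment follows completion of the screening assessments (section 4.3). The downside is that some values will be older than the last pre-treatment value, up to about 30 days before D0.

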9.1.4 Disposition of patients

The number of screened, included, randomised and treated patients will be given overall and according to the group which they belong to (if appropriate).

Eligibility criteria of treated patients will be checked. The number of treated patients who will complete or discontinue the study will be provided. Reasons for study discontinuation will be provided with detailed patient information.

9.1.5 Protocol deviations

Protocol deviations will be examined relative to criteria of inclusion and exclusion, and to compliance with the protocol with regard to administration of treatment and prohibited medications.

Major deviations will be defined, listed and summarized in the final statistical analysis plan issued prior to database lock.

9.2 Population to be analyzed

The Safety Population is defined as all included subjects receiving at least one DT infusion or at least one anti-cancer therapy or supportive care as BSC. For safety analyses, patients will be affected to the group of treatment they actually received.

The following populations are planned for the efficacy analyses:

- The Intent To Treat (ITT) Population : all randomized patients. In this population, patients will be analysed in their randomisation group whatever the treatment they received.
- The Per Protocol (PP) population includes all the patients of the ITT population without any major protocol deviation. Patients terminating the study prematurely will be included in the PP population provided that there is no protocol deviation. Before locking the database, the precise reasons for excluding patients from the PP dataset will be fully defined and documented by the Blind Review Committee.

9.3 Subjects characteristics

Subjects' characteristics will be evaluated according to demographic characteristics, physical examination, medical history and previous and concomitant treatments.

Demographic data will be summarized with usual descriptive statistics. Previous and concomitant treatments will be organised according to the WHO Drug dictionary. Parameters that cannot be easily organised by class will be listed individually.

9.4 Efficacy endpoints

9.4.1 Primary endpoint

The primary endpoint is overall survival (OS), defined as the time from the date of randomisation to the date of death from any cause. Patients without death at the time of the statistical analysis will be censored at the date they were last known to be alive.

The primary endpoint will be analyzed in ITT population (primary analysis), with an additional analysis in PP population.

Definition of date of death or censoring will refer to FDA guidelines for OS (definition including documented death only).

OS will be estimated using the Kaplan-Meier method and plotted as curves by treatment group.

The comparison between groups (pooled DT groups versus BSC) will be made using the unstratified LogRank test. The analysis will be performed when 285 events have been observed. The hierarchical sequential closed test procedure for a comparison of pooled DT groups with

BSC in the ITT Child Pugh A population will be used to control the overall type I error rate of 5%.

In addition to the analysis not adjusted for baseline characteristics considered above, a sensitivity analysis will be conducted using a Cox model adjusting for geographical region and pre-defined selected prognostic factors as recently described in this population such as ECOG score, BCLC stage, macroscopic vascular invasion, extrahepatic spread and hepatic impairment (Child Pugh score, prothrombine time) (Marrero J.A., 2013^[54], Reig M., 2013^[55], Iavarone M., 2015^[56]). HR, median and mean survival and OS rates every 3 months will be given with the corresponding 95% confidence intervals.

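### Should the primary overall-survival log-rank test have been stratified by Child-Pugh class or region?

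*Combined protocol and SAP*

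**What the plan says.** Section 9.4.1 specifies the test of overall survival in all randomised patients: "The comparison between groups (pooled DT groups versus BSC) will be made using the unstratified LogRank test". The synopsis and section 9.1.2 name the same unstratified test, and section 9.6 uses it again for dose selection. Section 4.3 stratifies randomisation by region only.

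Section 9.1.2 states that "Child Pugh status is a strong prognostic factor for OS in patients treated by sorafenib". It puts the control median and hazard ratio (HR) for the whole population at "median survival of the control group of 8 months and a hazard ratio of 0.69", and for Child-Pugh A, expected to be 85% of patients, at "median survival of the control group of 9 months and a hazard ratio of 0.68". It describes class A as a "homogeneous population of Child Pugh A patients from whom the clinical benefit is expected to be higher". The hierarchy evaluates "first the primary endpoint OS in the ITT population, then if statistically significant the primary endpoint OS in the ITT Child Pugh A population", followed by progression-free survival and response rate in class A.

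Both factors do appear in a supporting analysis. Section 9.4.1 adds that "a sensitivity analysis will be conducted using a Cox model adjusting for geographical region and pre-defined selected prognostic factors"; Child-Pugh score is one of the factors listed.

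**The concern.** A log-rank test that pools patients with very different prognoses is usually somewhat less powerful than one stratified by the prognostic factor. Here the protocol names such a factor, records it at screening (section 7.1) and already uses it to define the second test population, so stratifying would need no new data. The common convention of analysing as randomised also suggests having region in the primary test.

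The stakes are real in principle. If the first test fails, every later claim is closed, and the adjusted Cox model, being a sensitivity analysis, cannot reopen the hierarchy. Section 9.1.2 also says the plan was revised because of a risk of insufficient power.

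**Working it through.** **1. The plan's own power.** Inputs from section 9.1.2: 285 deaths, HR 0.69, two-sided 5%. From section 3: 1:1:1 allocation, so 2:1 for pooled DT against BSC. Schoenfeld's formula is power = Φ(√(D × 1/3 × 2/3) × |ln HR| − 1.960).

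- Overall: √(285 × 2/9) = 7.958; × 0.3711 = 2.953; − 1.960 = 0.993; power 84.0% (stated 85%).
- Child-Pugh A, 230 deaths, HR 0.68: √(230 × 2/9) = 7.149; × 0.3857 = 2.757; − 1.960 = 0.797; power 78.7% (stated 80%).
- Deaths needed for 85% at HR 0.69: Schoenfeld (1.960 + 1.036)² / (2/9 × 0.3711²) = 293.4; Freedman 8.978 × (1 + 2 × 0.69)² / (2 × 0.31²) = 264.6. The planned 285 lies between them.

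The planned power therefore belongs to the planned, unstratified test.

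**2. How different are the two classes on the planning figures?** The protocol gives no class B control median for this trial. With exponential survival in each class, 0.5 = 0.85 × 2^(−8/9) + 0.15 × 2^(−8/B). Since 0.85 × 0.5400 = 0.4590, 2^(−8/B) = 0.0410/0.15 = 0.273 and B = 4.27 months. The class B to class A hazard ratio is 9/4.27 = 2.1. Planning medians are whole months, so this is fragile: an overall median of 8.25 gives B = 5.18, and 8.5 gives B = 6.24.

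**3. Power of the first test, unstratified and stratified by Child-Pugh class.** Simulation of 390 patients, cut at 285 deaths, 40,000 runs per case. Assumed, not in the documents: exponential survival, accrual over 57 months, region shares 60/15/25% with no effect of region on survival, and the class B HR. Loss to follow-up was about 9.5%, close to the planned 10%. Monte Carlo error is about 0.2 point.

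| HR in A | HR in B | Unstratified | Stratified | Difference |
|---|---|---|---|---|
| 0.68 | 0.68 | 84.9% | 87.2% | +2.3 |
| 0.69 | 0.69 | 82.3% | 84.6% | +2.3 |
| 0.68 | 0.75 | 82.7% | 83.9% | +1.2 |
| 0.68 | 0.80 | 80.9% | 81.8% | +0.9 |
| 0.68 | 0.85 | 79.4% | 79.1% | −0.3 |
| 0.68 | 1.00 | 75.4% | 71.9% | −3.5 |

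Repeat simulations gave +1.9 to +2.3 for the first two rows. Break-even is at a class B HR of about 0.84. With HR 0.68 in both classes, an overall median of 8.25 months cuts the gain to 86.9 − 85.8 = 1.1 points, and 8.5 months to 87.2 − 86.9 = 0.3. If Child-Pugh class is not prognostic at all (HR 0.69), stratifying costs 85.0 − 84.7 = 0.3 point.

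The sign changes for a simple reason. If the effect is the same in both classes, surviving DT patients include relatively more of the high-risk class than surviving controls do, which dilutes the unstratified comparison. If the benefit sits mainly in class A, the surviving DT patients become richer in class A, and the unstratified test counts that real survival difference.

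**4. Passing both survival steps (all patients, then class A).**

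| HR in A / B | Unstratified | Stratified |
|---|---|---|
| 0.68 / 0.68 | 78.6% | 78.7% |
| 0.69 / 0.69 | 75.8% | 76.0% |
| 0.68 / 0.75 | 77.7% | 77.5% |
| 0.68 / 0.85 | 75.9% | 74.7% |

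Repeat simulations of the first row differed by −0.2 to +0.1 point. The class A test limits this probability, and stratifying the first test does not change it.

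**5. Region.** The documents give no survival figures by region. With no effect of region on survival, splitting class A by region as well takes off a further 0.3 to 0.7 point.

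**6. Validity.** With no treatment effect, two-sided rejection rates were 5.0 to 5.2% for the unstratified test and for both stratified versions.

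**The case for a change.** The best argument for stratifying is that failure at the first test closes everything, and about 2 points there would cost no patients or deaths. The two planning hazard ratios point to the favourable side. Weighting by deaths, ln 0.69 = (230/285) × ln 0.68 + (55/285) × ln HR(B) gives a class B HR of about 0.73, where the simulated gain was 1.6 points (83.5% to 85.1%). With the cited medians of 13 and 5 months as the prognostic contrast, the gain is 3.2 to 3.8 points.

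The arithmetic stands, but its force is limited. The 13-to-5 contrast is for Child-Pugh B patients treated with sorafenib, while section 4.1 admits only B7, so it may overstate the difference here. The implied 0.73 comes from two hazard ratios rounded to two decimals. Moving the common HR from 0.68 to 0.69 shifts unstratified power by 84.9 − 82.3 = 2.6 points, more than the gain at issue. Section 9.1.2 also expects more benefit in class A, which, read as a relative effect, is the direction in which the gain shrinks and then reverses.

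It is also true that the Cox model cannot rescue a failed first test. But it already shows whether the result survives adjustment for region and Child-Pugh score, so a stratified log-rank as a further sensitivity analysis would add little. Nor does analysing as randomised call for Child-Pugh strata, since randomisation was not stratified by class. Omitting the region stratum does not invalidate the test; if region is prognostic, the test is if anything slightly conservative.

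**Conclusion.** The concern does not hold. The unstratified log-rank is valid, is specified consistently, and is the test for which the stated power was calculated and approximately reproduces. On the planning figures, Child-Pugh stratification would change the power of the first test by about +2 points with equal effects in both classes, by nothing at a class B HR of about 0.84, and by −3.5 points with no effect in class B. It would not change the chance of winning both survival claims. Adding region has no demonstrated benefit.

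Against that uncertain return stands another late change to the primary test of an open-label trial. The synopsis anticipated the end of recruitment by the first quarter of 2017 and the final analysis in 2017, and section 9.1.2 records that the plan had already been revised after outside results. Keeping the simpler test is a reasonable choice.

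The figures rest on exponential survival within class, the back-solved class B median of 4.27 months, the assumed class B hazard ratios and accrual pattern, and no effect of region on survival. The finding that the test is valid does not depend on the assumed size of the class B effect.
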